8.5.5 Substudy Duration and Substudy Procedures

Subjects, clinicians, and key family members will participate in 2 telephone interviews, lasting approximately 1 hour each. Entry interviews will be conducted within 7 days from first investigational product dose (day 1); exit interviews will be conducted within 7 days prior to week 24 visit or within approximately 14 days post early termination visit. If possible, within 7 days from early termination notification will be targeted. **No protocol deviation will occur if these interviews are conducted outside of these timeframes.**

Subjects enrolled in Study 20190389 will be approached by clinic staff for recruitment and possible enrollment into this substudy.

At participating sites, subjects will be provided an option to opt-in to the qualitative interview substudy and be provided with additional information about the substudy either at time of screening for the main study or after enrollment and successful dosing with investigational product, depending on site preference. Clinical site staff will explain the substudy objectives and procedures to the subject and their selected key family member and obtain a supplementary written informed consent from each participant. Each subject and key family member will sign 2 copies of the consent form. Sites will send a

wet-ink version of the informed consent to Evidera, the third-party supplier who is performing the substudy, and will retain a copy of the signed informed consent for their study records. Clinic site staff will provide Evidera contact information for each participant enrolled in the substudy and Evidera will subsequently contact each participant to schedule interviews.

Once consent has been obtained, the subject ID and site details can be communicated by the site to the interview scheduler from Evidera along with potential dates for the day 1 and week 24 visits. The interview scheduler will obtain contact information and schedule tentative dates and times for the interviews with the subject, clinician, and key family member. Evidera will confirm with the site that the subject has completed study procedures for the day 1 and week 24 visits before confirming the interview dates and times of the interviews to ensure compliance to the substudy protocol.

Evidera staff, who are trained and experienced in qualitative data collection, will conduct telephone interviews using a semi-structured interview guide. Participants will be interviewed about the subject's pre-treatment status, any perceived changes during the study, and the meaningfulness of the changes experienced. During the interviews, interviewers will ask participants for specific examples to qualitatively illustrate the subjects' experience.

Participants will be specifically asked about the subject's functional abilities during and between migraine attacks after the start of the study; ie, perceptions of migraine, associated symptoms, and symptom impact/burden and interference on the subject's life; perceptions of meaningful changes in experience of migraine; and experience with treatment administration.

After open-ended questions, if participants do not mention concepts associated with the domains of the COA instrument in the clinical trial, the interviewer will specifically probe about those concepts. The interviewers will also explore what aspects of improvement or worsening of the subject's migraine (eg, frequency, severity, and duration) drove the changes, as well as the meaningfulness of change/no change reported by the subject.

8.5.6 Variables

8.5.6.1 Substudy Outcome Variable(s)

Qualitative data on changes resulting from treatment received in the open-label treatment period will be collected via telephone interview. Concepts that emerge from the qualitative interviews in relation to migraine impact, treatment efficacy, and migraine

experience will be the outcome. Data will be analyzed to achieve the study objectives, using qualitative data analysis software (ie, ATLAS.ti).

8.5.6.2 Exposure Variable(s)

Subjects will be started on the 70 mg dose of erenumab with provider discretion for dose optimization. Dose optimization will allow patients to remain on 70 mg, increase the dose from 70 to 140 mg and if needed decrease the dose back down from 140 to 70 mg. After week 12, all subjects are highly recommended to remain on the week 12 erenumab dose for the rest of the study. Dose changes are permitted at the investigator's discretion, but are not recommended unless medically necessary.

8.5.7 Substudy Data Analysis

Audio recordings from the interviews will be transcribed for qualitative analyses. Evidera will develop a separate data analysis plan that will detail how the qualitative data will be analyzed. The analyses of interview data will help to illustrate subjects' perceptions of meaningful change or difference, migraine functional impacts, and treatment efficacy or benefit. Subjects will be grouped by migraine type, and other exploratory subgroups may be determined based on the characteristics of the final sample. The qualitative report will discuss perceived treatment benefit and changes, if any, in relation to entry-interview discussion of the functional impacts of migraine.

A qualitative content analysis approach will be used to analyze data collected from qualitative interviews using coding dictionaries and ATLAS.ti qualitative data analysis software. The cleaned transcripts will be entered into ATLAS.ti qualitative analysis software version 7.0 or higher ([Friese and Ringmayr, 2013](#)). Qualitative data coded in ATLAS.ti can be systematically organized into analysis outputs. ATLAS.ti software is designed to facilitate the storage, coding, and retrieval of qualitative data.

Coding will be an iterative process that marks the beginning of the qualitative analysis process. Concept codes will be used to capture symptoms or impacts of the disease most important and relevant to participants. Qualitative data will be coded according to the coding dictionary as outlined in the analysis plan. The initial coding dictionary will be based on the structure of the main themes and content of the discussion guide to allow the text data to be coded with key concepts codes. The coding dictionary will be iteratively updated with emerging themes and concepts from discussions.

Evidera proposes to conduct longitudinal qualitative research analyses ([Calman et al, 2013; Saldana, 2003](#)), which is distinguished from a traditional qualitative approach by

the fact that the key focus of analysis is on how and why the subject experiences/ perceptions change over time. This innovative approach will be used to characterize changes in subjects' perceptions and experiences over time, particularly in concepts the subjects perceive as most important.

A list of each key concept identified at analysis of entry interviews will be provided to interviewers ahead of the follow-up interviews, so that these may be probed at the follow-up interviews. For each concept, a category will be assigned to show changes in concepts that occurred between the 2 time points (newly emerged, not changed/stable, improved, worsened, not experienced anymore, and missing) in the concept tracker. Each of the concepts probed during the follow-up interviews will be categorized and compared to the entry interview. An analysis will then be conducted on the data from groups of participants to document the changes observed over time.

All analysis and reporting will be conducted by Evidera staff with experience in qualitative research.

Subject characteristics collected in the clinical trial will be summarized for describing the sample. Descriptive statistics (eg, n, mean, SD, and/or frequency) will be used to characterize the sample in terms of questionnaire data, sociodemographic, and clinical characteristics.

The results of this sub-study will be reported separately from the main study.

8.5.8 Collection of Safety Information and Product Complaints

There will be no substudy-specific safety database for collection, recording, and reporting of adverse events reported during the conduct of the substudy. All safety data collection, recording, and reporting will be performed through the parent study and will follow the detailed procedures outlined in Study Protocol 20190389. Adverse events, serious adverse events, or product complaints reported during the conduct of an interview will be reported to Amgen and to investigational sites within 1 business day of awareness.

8.5.8.1 Definition of Safety Events

Refer to [Section 11.4](#) for definition of safety events.

8.5.8.2 Safety Reporting Requirements

The clinical site investigator is responsible for ensuring that safety events (adverse events, product complaints, and other safety findings) are reported in accordance with Amgen's Study 20190389 protocol. Evidera will report any adverse events to the clinical

site and Amgen within 1 business day of awareness; the site investigator will be responsible for reconciling the reporting to Amgen.

Safety events must be submitted as individual case safety reports to Amgen via the applicable Amgen Safety Reporting Form (paper or electronic form) which will be the responsibility of the subject's clinic site in accordance with the Study 20190389 protocol.

9. Statistical Considerations

9.1 Statistical Hypotheses

The study is descriptive in nature without a comparator arm, and as such no formal statistical hypothesis is defined.

9.2 Sample Size Determination

The total sample size of approximately 322 subjects (effective sample size of 289 assuming 10% dropout at week 24) is driven by the precision of the proportion estimates for the binary secondary endpoints, which targets a half-width of 95% confidence intervals (CIs) around 5%. The half-width of the 95% CI will be the widest when the estimated percentage is 50% given a fixed sample size and will become narrower if the percentage moves further away from 50% (see [Table 9-1](#)).

Table 9-1. Half-width of 95% CI for Various Estimated Percentages With Effective Sample Size of 289 Subjects

Percentage estimate	Half-width of 95% CI with effective sample size = 289
50%	5.8%
60%	5.6%
70%	5.3%
80%	4.6%

9.3 Populations for Analysis

The following populations are defined:

Population	Description
Full Analysis Set	The full analysis set (FAS) consists of all subjects enrolled in the study. Analysis of disposition, demographic and baseline characteristics, and important protocol deviations will utilize the FAS.
Efficacy Analysis Set	The respective efficacy analysis set consists of a subset of subjects from FAS who receive at least 1 dose of investigational product and have a baseline value and at least 1 post baseline value for the endpoint of interest. Analysis of the primary and secondary efficacy endpoints (except for the global impression Patient Reported Outcomes [PRO] endpoints) will utilize the respective efficacy analysis set.
Global Impression PRO Analysis Set	The global impression PRO analysis set consists of a subset of subjects from FAS who receive at least 1 dose of investigational product and have at least 1 post baseline value for the global impression PRO endpoints of interest . Analysis of each of the 3 global impression PRO endpoints will utilize this analysis set.
Safety Analysis Set	The safety analysis set (SAS) will consist of a subset of subjects from FAS who received at least 1 dose of investigational product. Analysis of safety endpoints and summary of investigational product administration will utilize the safety analysis set.

9.3.1 Covariates

All model-adjusted analyses of primary and secondary efficacy endpoints will include the corresponding baseline value for the endpoint being analyzed, **if applicable**, and baseline MMD.

9.3.2 Subgroups

The primary and secondary endpoints will be analyzed in the following subgroups:

- Whether remained on standard of care migraine preventive treatment throughout the study (yes vs no)
- Migraine type (EM vs CM) based on eDiary collection during baseline

The subgroups will be re-examined for appropriateness and may be re-categorized (due to small sample size, for example, if there are < 10% of subjects within a subgroup) before final analysis.

9.4 Statistical Analyses

The statistical analysis plan will be developed and finalized before database lock. Below is a summary of the timing and methods for the planned statistical analyses.

9.4.1 Planned Analyses

9.4.1.1 Interim Analysis and Early Stopping Guidelines

Not applicable.

9.4.1.2 Primary Analysis

Not applicable.

9.4.1.3 Final Analysis

The final analysis will be conducted when all enrolled subjects have completed the week 24/EOS visit **and the data have been entered, cleaned, and locked**.

9.4.2 Methods of Analyses

9.4.2.1 General Considerations

Summary statistics will be computed at each timepoint of interest. For continuous endpoints, the following descriptive statistics will be computed: number of observations, means, standard deviations, standard errors, medians, first and third quartiles, minimums and maximums. For categorical endpoints, the summaries will contain the number and percentage of subjects in each category.

Due to lack of a control arm, all analyses should be considered as descriptive in nature. Data on any endpoints collected after treatment discontinuation due to lack of efficacy or adverse event will be defined based on the worst observed value (for continuous endpoints) or non-response (for binary endpoints) using a composite strategy. Data collected after treatment discontinuation due to other reasons will be censored based on a hypothetical strategy and not be used in efficacy analyses as described in [Section 9.4.2.2](#).

9.4.2.2 Efficacy Analyses

Endpoint/ Estimand	Statistical Analysis Methods
Primary	
In the event of IP discontinuation due to lack of efficacy or adverse event, the TSQM overall satisfaction scale score after treatment discontinuation will be defined as the worst postbaseline value observed up to IP discontinuation (inclusive). Any TSQM data collected after treatment discontinuation due to other reasons will be censored and not included in the analysis.
 
The primary endpoint will be analyzed using a repeated measures mixed effects model, including baseline TSQM overall satisfaction scale score, visit, the prevailing erenumab dose from week 12 onwards, and baseline MMD based on observed data. The mean change from baseline in TSQM overall satisfaction scale score at week 24 will be estimated from the least-squares mean (LSM) of the mixed effects model, and the corresponding 95% CI will be provided. The nominal p-value will be reported by comparing the mean change from baseline in TSQM overall satisfaction scale score at week 24 to zero with a two-sided 5% significance level.

Secondary	
In the event of IP discontinuation due to lack of efficacy or adverse event, the binary secondary endpoint after IP discontinuation will be classified as not achieving overall satisfaction or global impression on improvement; and the continuous MFIQ domain scores after treatment discontinuation will be defined as the worst postbaseline value observed before treatment discontinuation. Data collected after IP discontinuation due to other reasons will be censored and not included in the analysis.
 
A generalized linear mixed effects model with the appropriate link function will be used to analyze each secondary endpoint based on observed data. The model will include the corresponding baseline value for the endpoint being analyzed (except for the global impression endpoints), visit, the prevailing erenumab dose from week 12 onwards, and baseline MMD.
 
For binary secondary endpoints, logit link function will be used, and the proportions and the corresponding 95% CI at week 24 will be estimated from the LSM (with inverse link function) of the mixed effects model.
 
For the continuous MFIQ domain score endpoints, identity link function will be used, and mean change from baseline in each domain score at week 24 with the corresponding 95% CI will be estimated from the LSM of the mixed effects model, and p-values comparing with zero at a 2-sided 5% significance level will be reported.

Exploratory	Will be described in the statistical analysis plan (SAP) finalized before database lock

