TSQM version 1.4			X			X	X	X	X	TSQM will assess satisfaction with standard of care migraine preventive medication at day 1 and only investigational product at subsequent time points.
STUDY TREATMENT										
Amgen investigational product administration ^e			X	X	X	X	X	X		

Footnotes are defined on the last page of this table.

Table 1-1. Subject Study Visits Through Open-Label Treatment Phase

PROCEDURE	Screening (up to 3 weeks before baseline) ^c	Baseline (4-5 weeks before day 1) ^c	Open-label Treatment Period (24 weeks)							Notes
			Day 1 ^e	Week 4	Week 8	Week 12	Week 16	Week 20	Week 24/ EOS	
STUDY VISITS										
Onsite visit ^a	X	X	X			X			X	
Remote visit – site staff phone call with subject ^b				X	X		X	X		

Page 3 of 3

BMI = body mass index; eDiary = electronic diary; EOS = End of Study; ETS = Expectation of Treatment Scale; GAD-7 = General Anxiety Disorder Scale;

MFIQ = Migraine Functional Impact Questionnaire; mGI-I = Migraine Global Impression Item; MIBS-4 = Migraine Interictal Burden Scale; MSSS = Migraine Symptom Severity Scale; PHQ-9 = Patient Health Questionnaire; TSQM = Treatment Satisfaction Questionnaire for Medication

^a Screening, Baseline, day 1, week 12, and week 24/EOS visits are required to take place onsite. Subjects will be provided the doses necessary to continue erenumab monthly treatment at a non-investigative site (eg, subject's home). Additional onsite visits are optional at the investigator's discretion.

^b For remote visits (ie, visits not conducted onsite), visit data will be collected by site staff via telephone or via electronic device as applicable (eg, clinical outcomes assessments).

^c Baseline may start on the same day as the screening visit.

^d Screening PHQ-9 is to assess eligibility and will be collected on a paper form. On-study PHQ-9 assessments will be collected on the subject's eDiary device.

^e All day 1 procedures must be completed before investigational product is administered.

Table 1-2. Schedule of Activities for Key Family Members

PROCEDURE	Screening (up to 3 weeks before baseline) ^a	Baseline (4-5 weeks before day 1) ^a	Open-Label Treatment Period (24 weeks)							Notes
			Day 1	Week 4	Week 8	Week 12	Week 16	Week 20	Week 24/ EOS	
GENERAL ASSESSMENTS										
Informed consent for key family members		X								Signing of informed consent can occur any time at or before the week 12 visit. Informed consent must be signed before the week 12 mGI-I is administered.

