- There are 2 intercurrent events, discontinuation of IP due to lack of efficacy or adverse event, and discontinuation of IP due to other reasons. The treatment effect of interest will be assessed for all subjects who receive at least 1 dose of IP and have a baseline value and at least 1 post-baseline value of the respective MFIQ domain scores. A composite strategy will be used for subjects who discontinued IP due to lack of efficacy or adverse event with data after IP discontinuation defined by the worst postbaseline value observed up to IP discontinuation (inclusive). A hypothetical strategy will be used for those subjects who discontinued IP due to other reasons with data collected after IP discontinuation censored.
- The treatment, which is erenumab 70 or 140 mg every 4 weeks
- The summary measure, which is change from baseline in each MFIQ domain score at week 24

The estimand for the secondary efficacy objective on subject functional impairment is the change from baseline at week 24 in each MFIQ domain score, in subjects with EM or CM who are currently on 1 standard of care migraine prevention therapy and who receive at least 1 dose of IP and have a baseline value and at least 1 post-baseline value in each MFIQ domain score, and a composite strategy will be used for subjects who discontinued IP due to lack of efficacy or adverse event with data after IP discontinuation defined by the worst postbaseline value observed up to IP discontinuation (inclusive), while a hypothetical strategy will be used for those subjects who discontinued IP due to other reasons with data collected after IP discontinuation censored.

Exploratory	

 To explore the effect of erenumab on the change from baseline in monthly medication-specific treatment satisfaction 	
 Change from baseline in TSQM overall satisfaction scale score at weeks 12, 16, and 20 and mean over weeks 16, 20, and 24 Change from baseline in TSQM sub-scale domain scores at weeks 12, 16, 20 and 24 and mean over weeks 16, 20, and 24: 
 effectiveness side effects convenience

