
 To explore the effect of erenumab on monthly global impression of improvement in migraine 	
 Improvement in subject global impression at weeks 12, 16, and 20, as defined by subject reporting of much improved or a little improved on the mGI-I Improvement in treating clinician's global impression at weeks 12, 16, and 20, as defined by treating clinician's reporting of much improved or a little improved on the mGI-I Improvement in key family member's global impression at weeks 12, 16, and 20, as defined by key family member's reporting of much improved or a little improved on the mGI-I

 To explore the effect of erenumab on the change from baseline in monthly functional impairment 	
 Change from baseline in MFIQ functional impairment domain scores, at weeks 12, 16, and 20, and mean over weeks 16, 20, and 24: 
 Impact on physical function Impact on usual activities Impact on emotional function Impact on social function

 To explore the effect of erenumab on the change from baseline in the burden of migraine 	
 Change from baseline in the Migraine Symptom Severity Scale (MSSS) total score at weeks 12, 16, 20, and 24 and mean over weeks 16, 20, and 24 Change from baseline in the Migraine Interictal Burden Scale (MIBS-4) total

	score at weeks 12, 16, 20, and 24 and mean over weeks 16, 20, and 24

 To explore the effect of erenumab on the change from baseline in number of monthly migraine days (MMD) 	
 Change from baseline in mean MMD over weeks 16, 20, and 24 Change from baseline in MMD at weeks 16, 20, and 24 Achievement of at least a 50% reduction from baseline in mean MMD over weeks 16, 20, and 24 Achievement of at least a 50% reduction from baseline in MMD at weeks 16, 20, and 24

 To explore the effect of erenumab on the change from baseline in acute migraine-specific medication use 	
 Change from baseline in mean monthly acute migraine-specific medication days over weeks 16, 20, and 24 Change from baseline in monthly acute migraine-specific medication days at weeks 16, 20, and 24

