All clinical outcomes assessments (COAs) detailed in the Schedule of Activities ([Table 1-1](#)) will be performed on the subject's eDiary device regardless of visit location.

The treating clinician and a key family member (if available) for each participating subject will be invited to complete an mGI-I at weeks 12, 16, 20, and 24/EOS. The key family member should be a person in the subject's life with whom s/he interacts significantly on a day-to-day basis. This person should have a deep understanding of the impact migraine has on the subject. They should also be able to provide their perspective of change in the subject's migraines over time. The person the subject chooses to nominate can be anyone such as a spouse, daughter or son, parent, sibling, or other relative or the person with whom the subject is in a de facto relationship. The key family member must sign an informed consent before completing any study-specific procedures. The same clinician and key family member of each subject should complete the mGI-I across all visits. If the clinician or key family member is unable to complete a visit, the assessment for that visit should be noted as missed.

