5.3 Study Points of Reference

Baseline Assessment

Baseline assessment for the endpoint of the interest is defined as the last non-missing measurement taken or the monthly interval assessed (for endpoints derived from daily eDiary collection during baseline period) before the first dose of investigational product. In cases where baseline measurements are taken on the same day as IP, it will be assumed that these measurements are taken prior to IP being administered.

Study Day 1

Study Day 1 is defined as the first IP dose date **or enrollment date if no IP received**.

Study Day

Study Day is defined as the number of days from Study Day 1.

Before Study Day 1:

Study Day = (Date of Interest – Date of Study Day 1)

On or after Study Day 1:

Study Day = (Date of Interest – Date of Study Day 1) + 1

Therefore, the day prior to Study Day 1 is -1.

Treatment Discontinuation Visit

Treatment discontinuation visit is defined as the earliest visit on or after the date when the decision to discontinue treatment is made.

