9.1 General Considerations

Summary statistics will be computed at each timepoint of interest. For continuous endpoints, the following descriptive statistics will be computed: number of observations, means, standard deviations, standard errors, medians, first and third quartiles, minimums and maximums. For categorical endpoints, the summaries will contain the number and percentage of subjects in each category.

Due to lack of a control arm, all analyses should be considered as descriptive in nature. If a subject discontinued treatment due to lack of efficacy or adverse event, data on primary and secondary efficacy endpoints collected after treatment discontinuation will be defined based on the worst post-baseline value observed (for continuous endpoints) up to IP discontinuation (inclusive) or non-response (for binary endpoints) using a composite strategy. If a subject discontinued treatment due to other reasons, data collected after treatment discontinuation visit will be censored based on a hypothetical strategy and not be used in efficacy analyses as described in [Section 9.5](#).

Analysis for primary and secondary endpoints will be using observed data with intercurrent event handling; analysis for exploratory endpoints will be using observed data without intercurrent event handling. A sensitivity analysis using observed data without any intercurrent event handling will also be performed for primary endpoint.

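### The composite rule for the primary and MFIQ endpoints has no value to assign to subjects who stop erenumab for lack of efficacy or an adverse event by about week 8 and stay on study

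*Protocol*

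**What the plan says.** **Schedule.** Protocol Table 1-1 places TSQM and MFIQ on day 1 and at weeks 12, 16, 20 and 24/EOS. The week 4 and week 8 contacts are phone calls without either. The endpoint list in Protocol Section 3 matches: "Change from baseline in TSQM overall satisfaction scale score at weeks 12, 16, and 20 and mean over weeks 16, 20, and 24" and "Change from baseline in MFIQ functional impairment domain scores, at weeks 12, 16, and 20, and mean over weeks 16, 20, and 24". The Table 1-1 note on TSQM adds: "TSQM will assess satisfaction with standard of care migraine preventive medication at day 1 and only investigational product at subsequent time points".

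**Composite rule.** For the primary endpoint after a stop for lack of efficacy or an adverse event, Protocol 9.4.2.2 says "the TSQM overall satisfaction scale score after treatment discontinuation will be defined as the worst postbaseline value observed up to IP discontinuation (inclusive"). SAP 9.1 applies the same rule to primary and secondary continuous endpoints: "worst post-baseline value observed (for continuous endpoints) up to IP discontinuation (inclusive"). Two other wordings exist. Protocol 9.4.2.1 speaks only of the worst observed value, with no post-baseline or timing limit. The secondary row of Protocol 9.4.2.2 limits MFIQ to values before the stop, while the MFIQ estimand includes the stop.

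**Visit definition.** SAP 5.3: "Treatment discontinuation visit is defined as the earliest visit on or after the date when the decision to discontinue treatment is made".

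**Who is analysed.** SAP 6.2 defines the efficacy set as everyone with at least one dose. SAP 9.5 defines the dose covariate even for subjects with no dose from week 12. The estimand text (Protocol Section 3, SAP 2.1) still requires at least one post-baseline score. Protocol 7.1 strongly urges keeping subjects on study after they stop the drug.

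**The concern.** Stopping early because the drug did not help or was not tolerated is a plain form of dissatisfaction with it. The composite strategy exists to count that event as a poor outcome. For the binary endpoints it does so, because the event is itself non-response and needs no earlier measurement. For the continuous endpoints the rule has to find an earlier on-study score, and the schedule produces none in the first half of treatment.

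Take a subject who stops at week 5 and stays on study. The next visit is the week 8 call, which has no TSQM. The week 12 to 24 scores are collected, and the rule says they are to be replaced, but there is nothing to replace them with. If a programmer follows the text, they become missing, and a repeated measures model uses nothing from a subject with no post-baseline outcome. This subject does have post-baseline TSQM scores, so he or she meets the estimand's own population condition.

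The same event would then count as failure on TSQM item 14 and be absent from the primary score, which item 14 helps to form. The choice would fall to whoever programs the analysis, after the data are in.

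**Working it through.** **1. The plan's own calculations.** The only design figures are CI half-widths for proportions. 1.96 × √(p(1−p)/n) for p = 50/60/70/80% gives 5.77/5.65/5.28/4.61% at n = 289 and 6.67/6.53/6.11/5.33% at n = 216. All eight agree with Protocol Table 9-1 and SAP Tables 3-1 and 3-2. Nothing is calculated for the primary endpoint or for early stops.

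**2. Which subjects have a value.** All rows concern stops for lack of efficacy or an adverse event. Week 8 is day 8 × 7 + 1 = 57; week 12 is day 85.

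| Situation | Score available to the rule |
|---|---|
| Decision by the week 8 visit, stays on study | None |
| Decision after week 8 and before week 12, stays on study | Week 12 score, if the inclusive limit means the discontinuation visit of SAP 5.3 and no unscheduled visit comes first; none if it means the decision date |
| Leaves the study before the first window | An EOS score is due (Protocol 8.1.3), but it falls before day 79 (TSQM, SAP Table 5-6) or day 72 (MFIQ, SAP Table 5-3); the SAP does not say whether the rule may use it |
| Stops after the week 12 assessment | Yes |

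SAP 8.3 gives no imputation for a missing TSQM or MFIQ score, and the models use observed data.

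**3. Share of pre-week-12 stops without a value.** On the decision-date reading it is all of them, unless a score happens to have been taken by that date. On the visit reading, with stops spread evenly over 84 days and all subjects staying on study (both assumed), it is 57/84 = 68%. If a share e has a usable early EOS score, it is 68% × (1 − e): 61% for e = 10%, 51% for 25%, 34% for 50%.

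**4. Effect on the week 24 mean.** Let f be the share of treated subjects left without a value, and g the gap between the mean change of the others (M) and the change these subjects should have been given. The mean over all treated subjects is M − f × g, so leaving them out shifts the result by f × g.

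| f (of 240) | g = 20 | g = 40 |
|---|---|---|
| 2% (about 5) | 0.4 | 0.8 |
| 6% (about 14) | 1.2 | 2.4 |

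A simulation (240 subjects, SD 25, visit correlation 0.6, all assumed) gave shifts of 1.0 for f = 5%, g = 20 and 2.0 for f = 5%, g = 40, in line with f × g.

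For scale, the 95% CI half-width of a mean at n = 216 is 1.96 × SD/√216: 2.67, 3.33 and 4.00 points for an assumed SD of 20, 25 and 30. At SD 25 the illustrated shift is 0.4/3.33 = 12% to 2.4/3.33 = 72% of it.

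**The case against.** The case for leaving the plan alone has several parts.

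- **The rule reaches further than it seems.** If the inclusive limit means the discontinuation visit, a subject who decides to stop after week 8 can be given the week 12 score. This stands. A reader might infer that the rule works only for subjects who stay on drug to week 12, or that it fails for most early stops. The first does not follow on the visit reading, and the second depends on when stops occur, which the documents do not report.
- **Early leavers do complete a TSQM.** This stands too. The windows assign scores to analysis visits; the composite rule is not limited to windowed scores. It would be wrong to say that the SAP discards these scores. It is silent.
- **The looser wording in Protocol 9.4.2.1 could supply a value**, either baseline or a later score. But Protocol 9.4.2.2, the estimand and SAP 9.1 all say post-baseline and up to the stop. The conflict needs settling and does not close the gap.
- **The estimand excludes subjects with no post-baseline score.** True for those who leave without one. It does not cover subjects who stay and are assessed from week 12.
- **Few subjects will be affected.** Possibly. Protocol 2.3 describes low discontinuation rates, and the plan assumes 10% dropout by week 24, so 6% for these two reasons before a first TSQM is a high upper end. Study dropout and stopping the drug are different events, however.
- **Other outputs show the issue.** SAP 9.1 adds a sensitivity analysis without intercurrent-event handling, and SAP 9.2 tabulates reasons for stopping. The sensitivity analysis keeps off-drug scores and does not estimate the composite estimand. A reader might infer that the primary result must be the more favourable of the two; that is possible, but the documents do not establish it.

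The study is single-arm and descriptive, which lowers the stakes. It does not supply the missing value.

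**Conclusion.** The gap is real but bounded. For subjects who stop for lack of efficacy or an adverse event by about the week 8 visit and stay on study, the rule for the primary and the four MFIQ domain endpoints has no value to assign. For early leavers it is undecided whether the EOS score counts. SAP 6.2 and 9.5 show that such subjects are expected in the analysis, yet they have no continuous outcome under the stated rule.

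Dropping them is what literal programming produces; no text orders it. The resulting bias is probably favourable, provided early failures would have scored worse than the rest. Its size cannot be fixed from the documents: 0.4 to 2.4 TSQM points is an illustration from an assumed 2-6% affected and an assumed 20-40 point gap, and the comparison with the CI width also rests on an assumed SD. The point should be settled before database lock.

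**What to change.** 1. **Collection.** In Protocol Table 1-1, require TSQM and MFIQ at the treatment discontinuation visit, remote visits included. Protocol 4.1 already says that clinical outcome assessments "will be performed on the subject's eDiary device regardless of visit location". With enrolment ended at 240 (SAP 3.2), this helps only subjects who have not yet passed that point.
2. **Rule.** In SAP 9.1 and Protocol 9.4.2.2, state that any post-baseline score at the discontinuation visit or an early EOS visit counts as within the limit, whatever its analysis window, and is carried to weeks 12 to 24. If there is none, assign a prespecified unfavourable value: for example a change of zero, or the worse of that and any later observed score (lower for TSQM, higher for MFIQ). Describe it as a composite failure value. A change of zero equals the day 1 score numerically, and day 1 TSQM rates standard of care, so it must not be presented as a rating of erenumab.
3. **Sensitivity and reporting.** Add an analysis that assigns the worst value of the scale (0 for TSQM, 100 for MFIQ), and report how many subjects the fallback affects.
4. **Wording.** Align Protocol 9.4.2.1, both rows of 9.4.2.2 and SAP 9.1. Reconcile the estimand's post-baseline requirement with SAP 6.2, so that it is clear whether the fallback covers dosed subjects with no score at all.

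The cost is a few sentences and a little programming. Items 2 to 4 need no new data. The reported mean change may come out slightly less favourable.
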